#### **Formulation**

The formulation of IMP in this study will be compounded using 250 mM [1-C]pyruvate and up to 3  $\mu$ M AH111501 sodium salt. The osmolality of this formulation is ~500 mosmol/kg. After compounding is completed, a sterile fluid path will be pre-filled with the IMP under aseptic conditions. The sterile fluid path itself will be manufactured and cleaned under aseptic conditions in accordance with GMP guidelines (ISO level 7). The pre-filled sterile fluid path and automated hyperpolarizer/quality control instrument (GE SPINLabTM) (see Appendix 5), placed in an adjacent room to the MR suite, will then be used to generate the final hyperpolarized [1-C] pyruvate contained within a syringe for rapid injection into the patient (see preparation methods below).

The IMP will be intravenously injected at a rate of 5 ml/second followed by a 20-ml saline flush at 5 ml/second. Prior to dosing, the injection line will be primed with saline solution and some of this will be flushed into the subject ahead of the IMP. In the case of unforeseen events, such as difficulties with the power injector, etc., hand injection will be allowed.

#### Supply and Packaging

Shipments containing kit supplies for IMP compounding will be provided by the manufacturer and shipped from their clinical supply unit. Site personnel at the clean room will be responsible for receiving kit supplies, compounding the IMP, filling the sterile fluid path using aseptic technique, performing quality control using the GE SPINLabTM instrument, and performing drug accountability. See preparation methods (below) and Appendix 5 for more information.

#### Storage

The investigators are responsible for ensuring that deliveries of IMP and other study materials from the manufacturer are correctly received, recorded, handled, and stored safely and properly in accordance with all applicable regulatory guidelines, and used only in accordance with this protocol. Pre-filled sterile fluid paths will be stored at -20 degrees C, and thawed prior to clinical use.

Refer to Appendix 3 (Handling and Storage Safety Data Sheet) for information.

#### Preparation Methods

IMP will be compounded under the supervision of a trained pharmacist, using a mixture of [1-C] pyruvate and AH111501 sodium salt. The mixture will be used to pre-fill a sterile fluid path using laser-welding technique under aseptic conditions in a clean room adjacent to the MR scanner. The pre-filled sterile fluid path will be stored frozen at -20 degrees Celsius until the time of clinical use at the treatment unit in the Surbeck lab ([name]) on the Mission Bay campus. At the time of clinical use, the sterile fluid path will be thawed using a warming module housed within the SPINLabTM instrument (see Appendix 5).

The hyperpolarization process will utilize the fully automated GE SPINLabTM hyperpolarizer, which will be situated in a room adjacent to the MR suite. The mixture of [1-C]pyruvate and AH111501 sodium salt will be hyperpolarized by DNP at low temperature (<1 degree K) using a 5T magnet and zero-helium loss cryogenics system. Following hyperpolarization, the IMP will be dissolved in sterile fluid water, diluted with TRIS/EDTA buffer solution, and forced through a C18

reverse-phase chromatographic column, which removes AH111501 to a level below 3  $\mu$ M, all in an automated fashion using the pre-fabricated sterile fluid path and SPINLabTM system. An integrated quality control (QC) system will analyze the IMP for pH, temperature, concentration, and polarization level, before it is approved for use by the local pharmacist. A sample of IMP will be collected for sterility testing. The final IMP is automatically collected within a syringe. The yield is expected to be ~50 mL of 250 mM [1-13C]pyruvate. Following approval for use from the pharmacist, the syringe containing IMP is delivered to the MRI scanning room and connected to the tubing connected to the infusion pump. The appropriate injection volume (per Appendix 2) is then delivered via the infusion pump to the subject at a rate of 5 ml/second. Note that for different preparations of [1-13C]pyruvate, the concentration may be slightly different than 250 mM. The current concentration and corresponding injection volumes are provided (Appendix 2). If a slightly different concentration of [1-C]pyruvate is available, the appropriate injection volume will be different but the amount of [1-13C]pyruvate injected will be unchanged. If this course of action is taken, the table corresponding to the updated injection volume will be placed in each patient's chart so that it is clear exactly what concentration and volume the patient received.

The IMP is a colorless to slightly colored, clear liquid.

Warning: Do not use the IMP if any particulates are visible in the solution.

Disposal: Unused substances can be disposed of by flushing down a normal sink using tap water.

For associated hazards and how to handle them, refer to Appendix 3 (Handling and Storage Safety Data Sheet).

#### Safety Information

Earlier studies of nonhyperpolarized pyruvate outside of the United States were summarized in section 1.2.1

Reported IMP-related AEs in previous studies in humans include:

Cardiovascular: dizziness, catheter site hematoma, heart rate increased, hypertension

Constitutional symptoms: hypoesthesia, unresponsive to stimuli, feeling hot/flushing, fatigue, feeling abnormal

Gastrointestinal: dysgeusia, dry mouth

Genitourinary: micturition urgency

Pain: catheter site pain

Pulmonary: pharyngolaryngeal pain

Neurologic: headache (migraine), parosmia

However, the quality of these prior studies was unclear. The findings from the phase I study of prostate cancer patients at UCSF, which included comprehensive safety monitoring, are summarized in the Background Section.

The dosage of IMP that will be used in this study, and the injection rate of 5 ml/second, have been shown to be safe and well tolerated in the phase I study completed at UCSF. Safety

monitoring included continuous lead 2 EKG monitoring for 10 minutes after injection, monitoring of vital signs, injection site, EKG, and adverse events, and laboratories for two hours after injection. Patients were also evaluated clinically 24 hours and 7 days after injection. No safety concerns were observed.

### 4.2 Drug Accountability

The Investigational Pharmacist will manage drug accountability records.

#### 4.3 Drug Ordering

UCSF will obtain supplies for IMP compounding directly from the manufacturer as study supply.

#### 5 Treatment Plan

#### Dosage and Administration

Each subject will receive HP C pyruvate injection at a dosage of 0.43 mL/kg body weight, the maximum administered dose in the phase I study. It will be injected intravenously at a rate of 5 mL/second followed by a 20 mL saline flush at 5 mL/second.

## 5.1 Early Stopping Rules for Safety

Toxicity will be reviewed on a continuous basis. In the event of one serious drug-related adverse event, enrollment will be halted for study safety review. If at any time (after two or more patients have been accrued) ≥33% of patients experience ≥grade 2 toxicity (excluding asymptomatic laboratory abnormalities deemed to be clinically insignificant by the PI or designee), accrual will be halted for further evaluation. At the time that it can be determined that continued accrual does not pose significant safety risks to patients, accrual may be re-initiated.

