## 3 Study Design

#### 3.1 Characteristics

This is a pilot prospective study to investigate the utility of HP C pyruvate MRI for assessing metabolism and monitoring early treatment response in patients with locally advanced or metastatic PDA. Patients will be enrolled in parallel in one of two cohorts:

Cohort A (N=20): Patients with locally advanced or metastatic PDA who are already on therapy will undergo hyperpolarized (HP) C pyruvate MRI at a single time-point.

Cohort B (N=20): Patients with locally advanced or metastatic PDA will undergo HP C pyruvate MRI at baseline prior to the initiation of a new line of therapy (standard-of-care first- or

second-line systemic therapies, radiotherapy, or therapies as part of a clinical trial), and again at 4 weeks (+/- 2 weeks) following treatment initiation.

In both Cohort A and B, patients may undergo an optional second dose of C pyruvate injection followed by MRI during the same imaging session.

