#### 3.7.1 Study Termination

The principal investigator reserves the right to terminate the study at any time.

Termination of the study will be considered in the event of any safety concerns arising at any time during the performance of the study.

The IRB must be promptly notified that the study will no longer be taking place and provided with a detailed written explanation.

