## 6 Study Procedures and Observations

The study-specific procedures and assessments are detailed in this section and outlined in the Study Calendar – Section 6.1.

The Screening procedures and assessments must be completed within 28 days of IMP administration, unless otherwise noted. Any results falling outside of the reference ranges may be repeated at the discretion of the investigator.

All on-study visit procedures are allowed a window of  $\pm$  5 days unless otherwise noted. Visit delays for public holidays or weather conditions do not constitute a protocol violation.

Protocol CC#: 20925

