## 6.3.2.2 Study Procedures, Follow-Up HP C pyruvate MRI (cohort B only)

For patients in Cohort B, a follow up HP 13C pyruvate MRI will be obtained as per above procedures at 4 weeks (+/- 2 weeks) following the initiation of systemic therapy or radiotherapy as per clinical care.

- Pre-Scan
  - o Clinical Assessments
    - Vital signs including blood pressure and heart rate

Before vital signs are measured, the subject should be resting for at least 5 minutes (if possible). The same position will be used each time vital signs are measured for a given subject and blood pressure will be measured from the arm contra-lateral to the site of IMP administration whenever possible.

Standard MR Scan

Patient is transferred to the MRI suite. Standard 1H MRI exam will be obtained in the abdomen, including T2 weighted imaging, and T1 weighted imaging pre and dynamically following gadolinium contrast administration (gadobutrol at 0.1ml/Kg body weight). If the patient has estimated glomerular filtration rate (eGFR) < 30, gadobutrol will not be administered.

- HP C MR Imaging
  - o Study Tx / Drug Admin: Hyperpolarized 13C pyruvate injection

Hyperpolarized 13C pyruvate will be injected intravenously at a dose of 0.43 mL/kg and at a rate of 5 mL/second followed by a 20 mL saline flush at 5 mL/second. The volume to be injected is based upon body weight and is outlined in Appendix 2.

- Imaging Procedures: Dynamic 13C MR imaging
  - 1-2 minutes post-injection
  - 13C 3D MRI sequence with Multiband spectral-spatial excitation pulse for minimal [1-13C] pyruvate saturation and echo-planar imaging (EPI) readout for accelerated spectral-spatial sampling.
  - An optional second HP 13C pyruvate injection and MRI acquisition will be performed within 15 to 60 minutes following completion of the first scan. This repeat injection and scan is optional. This second injection will only occur if there is no adverse reaction to the first injection. The optional second injection and MRI scan are used to assess the repeatability of tumor HP 13C pyruvate metabolism.

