#### 6.4 Supportive Care

Subjects should receive full supportive care as medically indicated.

The Principal Investigator or designee will be present during the administration and monitoring period.

Any events occurring during or subsequent to the administration of IMP will be addressed as required by the monitoring nurse and/or physician as deemed appropriate.

Additional toxicities that arise, including the determination that the injection administered was not sterile, will be treated at the discretion of the treating physician.

A site-specific, radiology tackle-box will be present at the imaging site. This tackle-box contains at a minimum: epinephrine 1mg/1ml, diphenhydramine 50 mg/ml, glucose tablets, NaCl 0.9% 500 ml bag, atropine 1mg/ml, methylprednisolone 125mg/2ml vial, phentolamine 5 mg vial, albuterol 5.5 gram inhaler, sterile water 10ml vial. Any patient who becomes unstable will be stabilized and transferred to the hospital by ambulance.

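### After one serious drug-related event, section 5.1 halts enrollment only; as written it does not suspend injections in patients already enrolled

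*Combined protocol and SAP*

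**What the plan says.** Section 5.1 of the combined protocol and SAP has two triggers.

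- For the first, "In the event of one serious drug-related adverse event, enrollment will be halted for study safety review".
- For the second, at least 33% of patients with grade 2 or higher toxicity once two or more have been accrued, "accrual will be halted for further evaluation".
- One restart sentence serves both: "At the time that it can be determined that continued accrual does not pose significant safety risks to patients, accrual may be re-initiated".

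All three sentences concern intake of patients. None mentions injections.

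The dosing provisions run separately and contain no exception for a halt.

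- For Cohort B, section 6.3.2.2 says: "a follow up HP 13C pyruvate MRI will be obtained as per above procedures at 4 weeks (+/- 2 weeks) following the initiation". The event meant is the start of the new treatment. The calendar in 6.1 carries the matching injection.
- For first injections, section 6 says: "The Screening procedures and assessments must be completed within 28 days of IMP administration, unless otherwise noted".
- Section 3.1 adds: "In both Cohort A and B, patients may undergo an optional second dose of" the agent in the same session. Sections 6.3.2.1 and 6.3.2.2 allow that repeat only if the same patient had no adverse reaction to the first injection.

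The general safeguards are these.

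- Section 3.7.1: "Termination of the study will be considered in the event of any safety concerns", and the principal investigator may terminate at any time.
- Section 6.4: "The Principal Investigator or designee will be present during the administration and monitoring period".
- Section 9.4 permits a change against an immediate hazard before ethics approval.

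**The concern.** A safety halt exists to limit exposure while a signal is examined. If a serious event is judged drug-related, the patients most directly concerned are the next ones to be injected, and those may already be enrolled. Under the present text, closing intake satisfies the rule, while an enrolled patient stays scheduled for the same agent at the same 0.43 mL/kg. Withholding a scheduled Cohort B follow-up would be the departure from the written procedure, not giving it.

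The scan is for research only. Section 6.3.2.2 says its result is not used to manage the patient, so pausing takes no clinical benefit away. A pre-specified stopping rule is the natural place to settle this, so that protection does not depend on someone deciding to act.

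**Working it through.** **Text check.** The plan gives no figure to reproduce here, so the first step is to ask whether any provision requires a dosing hold.

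- 5.1: halts and restarts intake only.
- 3.7.1: termination is to be considered; discretionary.
- 6.4: presence of the investigator or designee allows judgment but orders nothing.
- 7.5: stopping and re-challenge concern the patient who had the event.
- 9.4: an urgent amendment is permitted, not required.
- Appendix 4, sections 2 and 3.2: monthly site committee review, ongoing committee review of serious events, meetings every six weeks. These are review duties.
- Appendix 4, section 3.3: a notification duty. It names holding enrollment and stopping the study as separate actions, which tells against reading an enrollment halt as a dosing halt.

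No provision requires a hold.

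**Cohort B patients awaiting follow-up at a random date.** Expected number = Cohort B accrual rate x waiting time. Inputs: total accrual of 1 to 2 per month (3.6.1, 8.1.2) and a wait of 2 to 6 weeks after treatment start (6.3.2.2). Assumptions: accrual split evenly between cohorts (20 and 20 planned), no gap between baseline scan and treatment start, and 4.348 weeks per month. A real gap before treatment would raise these numbers.

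- Low: 0.5 per month x 2 / 4.348 = 0.23
- High: 1.0 per month x 6 / 4.348 = 1.38
- Planned pace: 20/36 = 0.556 per month x 4 / 4.348 = 0.51

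**How many come due during the review.** Section 5.1 sets no review length, so two assumptions are shown.

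1. The review ends at the next six-weekly committee meeting. Take the time to that meeting as uniform on 0 to 6 weeks and the remaining wait as uniform on 0 to W weeks (W at most 6). The share coming due first is 1 - (W/2)/6.
   - W = 2: 0.833, giving 0.23 x 0.833 = 0.19
   - W = 4: 0.667, giving 0.51 x 0.667 = 0.34
   - W = 6: 0.500, giving 1.38 x 0.500 = 0.69
2. The review takes 7 days (an illustration). The number coming due is rate x 7/30.44: 0.5 x 0.230 = 0.11 at the low rate, 0.556 x 0.230 = 0.13 at the planned pace, 1.0 x 0.230 = 0.23 at the high rate.

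**Enrolled but not yet injected, both cohorts.** Sections 3.4 and 6.2 do not tie enrollment to injection, but the gap between them is not stated. Using the 28-day screening window as a stand-in:

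- No gap: 0
- Full window at the higher accrual rate: 2 x 28/30.44 = 1.84

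**The second trigger, for comparison.** It fires on a single event at patient 2 (1/2 = 50%) or patient 3 (1/3 = 33.3%). Take the phase I rate of grade 2 toxicity, 1 of 31 (1.1.1).

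- Fires at patient 2: 1 - (30/31)^2 = 0.0635
- Fires at patient 3: (30/31)^2 x 1/31 = 0.0302
- Sum: 0.0937, out of 0.0968 over all looks from patient 2 to patient 40
- Other Cohort B patients expected by then at an even split: at most 0.5 and 1.0
- Expected exposures: 0.0635 x 0.5 + 0.0302 x 1.0 = 0.062 over the trial, at most

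**The case against.** The strongest reply is that an injection given unnoticed during an open review is implausible. The investigator or a designee attends every administration, may terminate at any time, and can change the protocol at once against a hazard. Toxicity is reviewed continuously (5.1), the committee reviews serious events on an ongoing basis, and a voluntary hold on enrollment must reach the committee's chair or vice chair and its director within one business day (Appendix 4, 3.3). A review could therefore end well before the next six-weekly meeting, which pulls the 0.2 to 0.7 down. The event itself may never occur: section 1.1 reports no serious events in the volunteer studies, the phase I table in 1.1.1 lists nothing above grade 2, and 1.2 reports no adverse effects in more than 20 human studies with two injections.

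Most of that stands. It limits the size of the problem. It does not supply the missing instruction, because each safeguard is discretionary, confined to the affected patient, or a duty to review or notify.

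Three stronger readings are tempting, and the documents do not support them.

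- A reader might count patients who may take the optional second injection as a third group still due the agent. Nobody is due that dose. It arises only within a baseline or follow-up session already counted, so it adds doses and not patients.
- A reader might want the same hold on the 33% trigger. That trigger would almost always fire on one grade 2 or higher event in the first two or three patients, and a hold there would avert about 0.06 exposures. Even the 1/31 rate is probably high, since 1.1.1 attributes that event more likely to an enema, which this protocol does not list.
- A reader might infer that patients will in fact be injected during a review. The text permits it; nothing shows that it would happen.

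**Conclusion.** The point holds for the serious-event trigger. Section 5.1 closes intake and leaves dosing of enrolled patients to discretion. Expected exposure is small: 0.2 to 1.4 Cohort B patients waiting at a random date (0.5 at the planned pace), of whom about 0.2 to 0.7 would come due if the review ran to the next committee meeting, and fewer if it were shorter. Between 0 and 1.8 further patients might be enrolled but not yet injected.

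These counts are conditional on a serious drug-related event, whose frequency cannot be estimated from the documents. They rest on an even cohort split, on no delay between baseline scan and treatment start, and on two proxies: the committee meeting interval for the length of the review, and the screening window for the gap between enrollment and injection. The textual finding depends on none of them. This is a cheap improvement to a participant-protection rule. It is not evidence that the agent or the trial is unsafe, and it alters no sample size or power calculation.

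**What to change.** Amend two places.

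- **Section 5.1, first trigger.** After one serious drug-related adverse event, halt enrollment and all further administration of the agent (baseline, Cohort B follow-up and optional repeat) until the safety review is complete. For this trigger, make the restart sentence cover dosing as well as accrual.
- **Section 6.3.2.2.** Make the follow-up injection conditional on no dosing hold being in force.

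Leave the trigger based on 33% of patients with grade 2 or higher toxicity unchanged.

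The drafting cost is a few sentences in one amendment. The scientific cost is that a Cohort B follow-up scan may be missed or fall outside its 4 +/- 2 week window during a review. That loses one of 20 planned pairs and leaves that patient's baseline injection without its counterpart. Section 8.1.2 allows extra subjects to reach the evaluable number, but 3.3 does not list a missed follow-up among the reasons for replacement, and a replacement exposes a new patient to two injections, or up to four with both optional repeats. The amendment should say whether such a patient may be replaced.

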## 6 Study Procedures and Observations

The study-specific procedures and assessments are detailed in this section and outlined in the Study Calendar – Section 6.1.

The Screening procedures and assessments must be completed within 28 days of IMP administration, unless otherwise noted. Any results falling outside of the reference ranges may be repeated at the discretion of the investigator.

All on-study visit procedures are allowed a window of  $\pm$  5 days unless otherwise noted. Visit delays for public holidays or weather conditions do not constitute a protocol violation.

Protocol CC#: 20925

## 6.1 Study Calendar

Period / Procedure	Screening	Baseline HP  C pyruvate MRI		Follow up HP  C pyruvate MRI  4w ± 2w post tx initiation			Follow-Up	
		Pre- scan	HP  C MR Imaging	Post-scan	Pre- scan	HP  C MR Imaging	Post- scan	2-3mo interval tx
Study Day / Visit Day	-28d - 0d							initiation
Study Tx / Drug Admin								
HP  C pyruvate injection			Х			X 		
Administrative Procedures								
Informed consent	Х							
Clinical Assessments								
Baseline conditions	Х							
Concomitant medications	Х							
Medical history/Demographics	Х							
Performance status	Х							
Vital signs	Х	Х		X 	X 		X 	
AE assessment				X 			X 	
Laboratory Assessment								
Serum creatinine	Х							
Imaging Procedures								
MR Scan			Х			X 		
Disease Assessment on SOC CT								X 

Vital signs will be collected at the end of the visit (once the final scan is completed). AEs will be assessed following each scan.

<sup>1 Cohort B only: For patients in Cohort B, a follow up HP 13C pyruvate MRI will be obtained as per above procedures at 4 weeks (+/- 2 weeks) following the initiation of systemic therapy or radiotherapy as per clinical care.

